# Summary

In the UK, ovarian cancer (OC) causes more deaths than all the other gynaecological cancers put together. Majority of patients present with advanced disease which is associated with poor survival. In contrast, five-year survival rates for women diagnosed with stage I OC are over 90%, suggesting that early detection through screening may impact on outcome. Preliminary data from screening trials supports this view. The UK Collaborative Trial of Ovarian Cancer Screening (UKCTOCS) is a multicentre randomised control trial which aims to assess the impact of screening on ovarian cancer mortality while comprehensively evaluating physical and psychological morbidity, compliance and resource implications of screening and performance characteristics of a serum CA125 versus ultrasound based screening strategy. Women aged 50 to 74 were randomly invited from age/sex registers of Primary Care Trusts adjoining 13 trial trial centres in England, Wales and Northern Ireland. Those who accepted the invitation were sent appointments to attend recruitment clinics. After confirmation of eligibility, 202,638 postmenopausal women were randomised between 2001 and 2005 to screening with transvaginal ultrasound (U/ultrasound group), serum CA125 interpreted using a 'Risk of Ovarian Cancer' algorithm (M/multimodal group) or control (C group) in a 1:1:2 ratio. Women in the U and M groups receive annual screening till the end of 2011 using well-defined strategies which incorporate repeat testing. If a persistent suspicious abnormality is noted, they undergo clinical assessment and surgery. All women are followed to the end of 2024 via a 'flagging' study' through the NHS Information Centre for Health and Social Care (formerly Office of National Statistics) and postal questionnaires. The sample size allows over 80% power at the (two-sided) 5% significance level to detect a reduction in ovarian cancer mortality of 30% in C versus M and U groups alone.

# Background

In the UK, ovarian cancer (OC) causes more deaths than all the other gynaecological cancers put together. In 2004 in England and Wales, it accounted for 6% of all female cancer deaths with 5,293 women dying of the disease. Whilst advances in therapy have improved median survival during the last decade, there has been little or no change in the overall mortality rate. 1,2

Stage is one of the most important determinants of survival with most patients presenting with advanced disease, possibly as a result of non specific symptoms and delays in diagnosis.  The small proportion of patients who are diagnosed with stage I OC have five-year survival rates in excess of 90%.  This suggests that early detection through screening may impact on outcome.

During the 1990s, large prospective studies of screening have demonstrated that both CA125 and ultrasound can detect OC in asymptomatic women. However, the impact on mortality of preclinical detection of OC by screening remains uncertain. Preliminary data supports optimism. In a randomised controlled trial of ovarian cancer screening (OCS), median survival in women with OC in the screened group (72.9 months) was significantly better when compared to the control group (41.8 months). Data from single arm prospective studies also suggest a possible survival benefit  although in these cases, lack a control group could lead to significant bias from a "healthy-volunteer effect".

Screening is not without morbidity. A proportion of women will undergo unnecessary surgery following false positive results and a few of these surgical procedures will lead to complications and rarely death. Secondly, there may be psychological sequelae resulting from screening, repeat testing and receiving false positive/negative results. Thirdly, there are major cost implications of a population screening programme. Resource implications, psychological sequelae and physical morbidity will be key factors in assessing the overall impact of OC screening.

In 1998, the NHS Centre for Reviews and Dissemination completed a systematic review which found that screening with ultrasound and serum CA125 can detect ovarian cancer in asymptomatic women but that the impact of screening on outcome is unproven. The recommendation was that screening should not be introduced into clinical practice until further information was available from randomised trials designed to document the impact of screening on OC mortality as well as the adverse effects and the cost effectiveness of screening.8 Based on this, the UK Exceptional Cases Advisory Committee concluded that a well designed trial of OCS would be of value to the National Health Service. Lay groups like OVACOME and the National Federation of Women's Institutes urged the UK government to support research into OCS. In parallel, it was clear that there was only a limited window of time to perform a randomised controlled trial (RCT) on the effectiveness of OCS before media publicity and demand from individuals, lay groups and sectors of the medical profession led to widespread implementation. The UK Collaborative Trial of Ovarian Cancer Screening (UKCTOCS) was set up in response to these needs and commenced recruitment in 2001.

#### **Trial Centres**

The trial is conducted through 13 trial centres (TC) in England, Wales and Northern Ireland which are mainly located in NHS Trusts. Each centre has a dedicated trial team consisting of a research nurse, phlebotomist, clerk and ultrasonographers led by a consultant clinician (Lead Researcher). The trial centres undertake recruitment of the participants and performance of the screening tests. The teams arrange clinical evaluation of women confirmed to have abnormalities on screening and referral to the appropriate NHS clinic if surgery is appropriate.

#### Aims of the trial

The overall aim of the UK Collaborative Trial of Ovarian Cancer Screening (UKCTOCS) is to provide data so that an informed decision about the introduction of population screening for ovarian cancer can be made.

#### Primary objective

To establish the impact of screening on ovarian cancer mortality by comparing disease mortality in the screen and control groups.

[figure not shown]
# Secondary objectives

- (1) To assess and compare the performance characteristics of the two screening strategies (serum CA125 versus ultrasound)
- (2) To determine the physical morbidity resulting from surgical intervention attributable to screening
- (3) To assess the psychological consequences of screening
- (4) To determine the resource implications of screening and the resulting interventions
- (5) To assess feasibility of screening, as reflected by compliance rates with annual screening
- (6) To establish a serum bank for future assessment of novel tumour markers

# Design

UKCTOCS is a RCT of postmenopausal women aged 50 to 74 years randomised to (1) Study group: There is a 1:1 randomisation within this group to (a) An ultrasound group (U, annual screening with transvaginal ultrasound) and (b) A multimodal group (M, annual screening with serum CA125 as a primary test and ultrasound as a secondary test). (Figure 1) (2) Control group: No screening

Figure 1: Trial design

#### Inclusion criteria

- (1) Age 50-74 years
- (2) Postmenopausal: This is defined as either (a) >12 months amenorrhoea following a natural menopause or hysterectomy, or (b) >12 months of hormone replacement therapy commenced for menopausal symptoms. The restriction is because premenopausal women have a greater incidence of benign and physiological conditions associated with false positive findings on multimodal and ultrasound screening. The criteria does not entirely exclude premenopausal women, but it is not feasible to determine FSH levels in all

volunteers and such an approach would not be applicable to women taking hormone replacement therapy.

# Exclusion criteria

- (1) Previous ovarian malignancy;
- (2) History of bilateral oophorectomy;
- (3) Active non-ovarian malignancy: Women who have a past history of malignancy are only eligible if (a) they have no documented persistent or recurrent disease and (b) have not received treatment for >12 months. The intention is to minimise false positive CA125 results due to advanced stages of previously diagnosed malignancy. This exclusion does not include premalignant disease such as cervical intraepithelial neoplasia or use of Tamoxifen to prevent breast cancer recurrence.
- (4) Increased risk of familial ovarian cancer: The high-risk women are eligible for a separate trial, the United Kingdom Familial Ovarian Cancer Screening Study (UKFOCSS). They are defined by the eligibility criteria for UKFOCSS. These women are first-degree (1°) relatives (mother, sister, daughter) of a cancer affected member of a "high risk" family. The high-risk family is defined by one of the following criteria:
  - Two or more individuals with OC who were 10 relatives
  - One individual with OC and 1 individual with breast cancer diagnosed under
     50 years who are 1º relatives
  - One individual with OC and 2 individuals with breast cancer diagnosed under
     60 years who are connected by 1º relationships

- An affected individual with a mutation of one of the known ovarian cancer predisposing genes (BRCA1, BRCA2, MSH1)
- One person with OC and three individuals with colorectal cancer with at least one case diagnosed before 50 years, all connected by 1º relationships.
- Affected relatives fulfilling criteria 1, 2 or 3 who are related by second degree through an unaffected intervening male relative
- (5) Participation in other ovarian cancer screening trials: It should be noted that after the start of UKCTOCS, there were no other OCS trials in the general population in the UK.

#### **Ethical issues**

The trial involves 13 Trial Centres (RC) and their adjoining Primary Care Trusts (PCT). Ethical approval was obtained from the North West Multicentre Research Ethics Committee on the 21st June 2000; MREC Reference 00/8/34. Site-specific approval was obtained from the individual Local Regional Ethics Committees of the trial centres and their adjoining Primary Care Trusts (PCT). Approval was also obtained from the Caldicott Guardians (data controllers) of each of the participating PCTs. The sponsor is University College London.

#### Recruitment

2,000 to 10,000 women aged between 50 and 74 years were randomly selected on a regular (usually 3 monthly) basis from the age/sex registers held by the participating PCTs using specialised software commissioned from the NHS. Their contact details, date of birth, NHS number and GP details were forwarded as an electronic file to the Coordinating

Centre (CC). The software ensured that the women selected were flagged on the PCT register such that their details were not included in future downloads. These files were uploaded into the TMS. Women were then sent personal invitations (Appendix B) to join the trial along with a brochure outlining the objectives, design and inclusion/ exclusion criteria. Women who returned the tear away slip were sent appointments to attend for recruitment along with a detailed trial information sheet (Appendix C).

At the recruitment appointment, women viewed an information video and participated in a group discussion. They completed an 18-item recruitment questionnaire (Appendix D), which included information regarding eligibility. Those who were willing to participate in the psychosocial study were given a set of baseline quality of life questionnaires to complete and return to the researchers in a pre-paid envelope (Appendix E-J). All volunteers provided a baseline serum sample that was sent overnight at room temperature to the CC laboratory (Tumour Marker Laboratory, UCL) for storage.

The recruitment questionnaires were sent to the CC where they were scanned electronically using computerised intelligent character and optical mark reading software (Cardiff Software Inc, Teleform Elite version 8.1.1) which allowed rapid and accurate data entry. Any inconsistency or information not recognised by the data capture software was verified manually by trained data entry staff, who validated the computer-interpreted data.

The TMS checked for completeness of eligibility data. When data was incomplete, women were placed 'on hold' and letters requesting further information were automatically be sent.

If the volunteer was placed 'on hold' because 12 months had not elapsed since her last

menstrual period or start of hormone replacement therapy, she was informed and included in the randomisation process when 12 months have elapsed from the relevant date. The TMS generated lists of women who had a family history suggestive of 'increased risk of ovarian cancer'. Such women were individually contacted and eligibility confirmed. If they fulfilled criteria which put them at 'increased risk' of familial ovarian cancer, their GP was sent a letter requesting that the individual be referred to the Clinical Genetics department for risk assessment.

## Consent

Separate written informed consent for the main trial, serum bank (Appendix K) and the psychosocial study was obtained (Appendix L). Each individual was also asked to sign a data protection form (Appendix M). A copy of the consent form was sent to the CC where it was checked and any exceptions to future use of data or samples noted on the TMS.

#### Randomisation

Once the TMS confirmed eligibility, participants were randomised to the control (C group), multimodal (CA125) (M group), or ultrasound (U) group in a 2;1:1 ratio using a computer generated random number algorithm. Randomisation was carried out as follows:

- (1) The TMS allocated a set of 32 random numbers to each RC
- (2) The lowest 8 were allocated to the M-group, the next 8 to the U-group and the remaining 16 to the C-group.
- (3) Each successive volunteer within the RC was randomly allocated one of the random numbers and hence randomised into a group
- (4) When all 32 random numbers had been used up a further set of 32 was generated

The randomisation was accomplished by using the visual basic randomisation statement and the Rnd function. Following this, letters were automatically printed and sent to the woman and her GP confirming eligibility and randomisation status.

#### Interventions

The screening strategies utilise two screening tests – serum CA125 interpreted the Risk of Ovarian Cancer (ROC algorithm and transvaginal ultrasound (TVS) of the ovaries.

# Screening tests

For the measurement of serum CA125, a blood sample is taken in Greiner gel tubes (8 mL gel separation serum tubes; Greiner Bio-One 455071, Stonehouse, UK) at the trial centre and transported overnight at ambient temperature to the central laboratory. The blood is centrifuged at 4,000 rpm for 10 minutes and the serum separated. Excess serum is aliquoted and stored. Serum CA125 levels are determined by commercial enzyme immunoassay on the Roche EIA Elecsys 2010 system. All blood samples received >56 hours after venepuncture are discarded and repeat samples requested.

The second test used is transvaginal ultrasound (TVS). Where this is not acceptable to a volunteer, transabdominal ultrasonography is performed. The scans are performed by two levels of staff. Annual and repeat scans following an unsatisfactory annual scan are performed by Level 1 sonographers who are certified ultrasonographers, or trained midwives or doctors with experience in gynaecological especially transvaginal scanning. Level II scans are performed when an abnormality is detected on the annual screen. Level II sonographers are experienced gynaecologists or radiologists or senior

ultrasonographers (usually at superintendent grade in the NHS) with particular expertise in transvaginal ultrasonography. Majority of the scans were performed on a dedicated trial ultrasound machine.

Ovarian morphology and dimensions are assessed and volume determined using the formula for an ovoid (d1  $\times$  d2  $\times$  d3  $\times$  0.532). Ovarian morphology is classified as

- (1) Normal: if the ovary is of uniform hypoechogenicity and smooth outline with or without a single inclusion cyst or spots of calcifications. To classify as normal the inclusion cyst must be single, less than 10mms and should not distort the outline of the ovary.
- (2) Simple cyst: A single, thin walled, anechoic cyst with no septa or papillary projections Is detected
- (3) Complex: All non-uniform ovarian echogenicity excluding single simple cyst. If there are more than one cyst even if these are without septae or papillations and have thin wall with regular internal outline, ovarian morphology is classified as complex.
- (4) Complex unchanged: Where the morphology is complex as described above but it has been noted and reviewed previously and has remained unchanged in appearance and size on follow up.

Detailed description of all features - the number and size of cysts, wall regularity, presence and thickness of septae, size of papillations and echogenicity of the fluid contents will be recorded (Appendix O). Definitions of ultrasound features and classification of cysts follow guidelines published by the International Ovarian Tumour Analysis (IOTA) group .

When ovaries are not visualised, ultrasonographer specify if a good view of iliac vessels is obtained or if the view is obscured (poor) due to bowel, fibroids, pelvic varicosities or other reasons.

Based on visualisation and morphology of the two ovaries, scans are classified as

- (1) Normal: If both ovaries have normal morphology or simple cysts <60cm^3 or are not visualised but a good view of the iliac vessels is obtained, or are complex unchanged.
- (2) Abnormal: If one or both ovaries have complex morphology or simple cysts >60 cm³ or ascites (vertical pool in Pouch of Douglas >10mms)
- (3) Unsatisfactory: If one or both ovaries are not visualised due to a poor view. The exception is those scans where one ovary is not visualised due to a poor view but the other ovary has abnormal morphology or a simple cyst >60 cm^3 or >5cms in diameter. In the latter case, the scan will be classified as abnormal.

Scan images are transferred weekly on magneto-optical discs for centrally archiving at the CC. TCs can request central review of the ultrasound image.

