Exploratory analysis: With women followed for up to 13 years in the first instance until 2014 and during extended follow-up until 2024 there is great scope to produce an extensive array of exploratory analyses. Characteristics of the randomised population will be compiled using standard descriptive statistics of the (baseline) recruitment data. In addition, the use of postcodes can provide relevant deprivation indices. These will be further enhanced by data obtained via from postal questionnaires. The collection from HSCIC of incidence data of all other cancer types and mortality data of all causes allows investigation of numerous potential links between incidence and mortality and the population characteristics.

The vast amount of data generated from the screens themselves, pertaining to ultrasounds, blood tests, surgery outcomes and histopathology results will be analysed as 1) a quality control of the screens (e.g. percentage of ovaries 'seen' by ultrasound sonographers) 2) as worthwhile scientific data in its own right (e.g. average ovarian volume) and 3) as further possible explanatory variables in studies on other cause mortality and incidence.

**Predefined subgroups**: The benefit of screening, and in particular the positive predictive value (PPV), will depend on the absolute level of risk for the population. Women at a particularly high risk of developing OC due to familial predisposition are excluded from this trial. Apart from differences between age groups, long-term use of oral contraceptive pills

and number of pregnancies are known to be factors influencing the risk of developing OC.

The major subgroups to be explored and contrasted will be those defined as being 'low

risk' and 'intermediate risk' groups within this population. The 'low risk' group will be

defined as women with >3 full-term pregnancies or >5 years use of oral contraceptives;

the 'intermediate risk' group will be those women with <3 full-term pregnancies and <5

years use of oral contraceptives.

Start date: April 2001

End of screening date: 31st December 2011

Censorship for primary mortality analysis: 31st December 2014

Reporting date for above: June 2015

End of follow-up: December 2024

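### The ovoid volume formula is printed with the constant 0.532, but three full diameters give pi/6 = 0.5236; if 0.532 was also used in calculation, volumes are 1.6% too large (minor).

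*Protocol*

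**What the plan says.** The Protocol's only volume formula is under Screening tests. It names the shape ("Ovarian morphology and dimensions are assessed and volume determined using the formula for an ovoid") and prints the product of three diameters, d1, d2 and d3, times 0.532. No source is given for the constant, and no other value appears elsewhere in the Protocol.

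Volume then appears in two places:

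- **Scan classification (same section).** A scan is normal in these circumstances, among others: "If both ovaries have normal morphology or simple cysts <60cm" (cubed). It is abnormal on this condition: "If one or both ovaries have complex morphology or simple cysts >60 cm³ or ascites". One exception to the unsatisfactory class also accepts a diameter instead of a volume: ">5cms in diameter. In the latter case, the scan will be classified as abnormal".
- **Exploratory analysis (Statistical analysis plan).** Screening data are to be analysed "as worthwhile scientific data in its own right (e.g. average ovarian volume").

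The scan form in Appendix O records ovarian dimensions and cyst dimensions. It shows no coefficient and no legible field for a computed volume.

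**The concern.** A formula that names its geometry fixes its own constant, and this constant is not the one that belongs to the named shape. The digits suggest a transposition of 0.523, although the Protocol cannot confirm that.

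The figure matters because it is an operating quantity and not background text. As the only volume formula given, it is the natural one to apply to the 60 cm³ limit. That limit helps decide whether a scan is abnormal. In the ultrasound group an abnormal Level I scan leads to a Level II scan. In both screened groups an abnormal Level II scan leads to clinical assessment. The formula also feeds directly into average ovarian volume as a reported result. A wrong constant acts in one direction only, so averaging over many scans does not remove it. Anyone reproducing volumes from the Protocol would carry it forward.

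**Working it through.** **Inputs.** From Screening tests: three diameters, an ovoid, the constant 0.532 and the simple-cyst limit of 60 cm³. Assumption: ovoid means an ellipsoid, and d1, d2 and d3 are its full diameters.

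**Constant for the named shape.** Volume = (4/3) × pi × (d1/2) × (d2/2) × (d3/2) = (pi/6) × d1 × d2 × d3, and pi/6 = 0.523599. A simulation with 10 million points gave 0.5235.

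**Attempt to reproduce 0.532.** The usual roundings and approximations are 0.5236, 0.5233, 0.523, 0.52 and 0.5. None of them gives 0.532, so the printed figure is not reproduced.

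**Size, if 0.532 was used in calculation:**

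- Ratio: 0.532 / 0.523599 = 1.01605, so volumes are 1.6% too large. Against 0.523 the excess is 1.7%.
- Correction factor: 0.523599 / 0.532 = 0.984.
- A recorded 60 cm³ corresponds to 60 × 0.523599 / 0.532 = 59.05 cm³ by pi/6.
- A pi/6 volume of 60 cm³ would be recorded as 60 × 1.01605 = 60.96 cm³.
- In diameter, for a spherical cyst: (60 / 0.523599)^(1/3) = 4.857 cm against (60 / 0.532)^(1/3) = 4.831 cm, a difference of about 0.26 mm.

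**Which scans could change class.** Only a simple cyst with a pi/6 volume between 59.05 and 60 cm³ could change, from normal to abnormal. Complex morphology, ascites, visualisation and the 5 cm diameter alternative use no volume and are unaffected.

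**Scale against measurement error.** For a 48.57 mm spherical cyst, a 1 mm change in one diameter changes the volume by 1 / 48.57 = 2.1%, which is more than the whole discrepancy. If each diameter carried an independent error of 3% to 5% (an assumption; the Protocol gives no figure), the volume error would be sqrt(3) × 3% = 5.2% to sqrt(3) × 5% = 8.7%.

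**Size, if 0.532 is only a slip in the text:** zero.

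**The case against.** The strongest reply is that nothing shows 0.532 was ever used. The scan form records dimensions and no coefficient, and the Protocol refers to a separate Ultrasound Screening Protocol for more detail, which is not at hand. If the figure is a typing slip, no volume is wrong. This stands, and it makes every statement of size conditional.

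The link to the 60 cm³ limit is also inferred. The formula is introduced for ovarian volume, and the classification text does not say how cyst volume is obtained. Nor does the Protocol say that the limit was set on pi/6 volumes. If one formula was used throughout, the limit was at least applied consistently. This stands too. The reply to it is only that no other volume formula is given.

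The effect is smaller than a 1 mm reading difference. That is true for a single scan, but random reading error tends to average out of a mean and a fixed factor does not.

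Ovoid is sometimes used loosely, and an egg shape need not have exactly the pi/6 constant. The Protocol offers no such derivation or source for 0.532, however, so this does not rescue the printed figure.

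A reader might infer that scan results as a whole are inflated by 1.6%, or that volumes already reported are certainly wrong. The Protocol supports neither. A scan result is a category, which can change only in the narrow band around the limit. The Protocol also does not show which constant any reported volume used.

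**Conclusion.** The Protocol is wrong as written, and the point is minor. The constant for the named shape is pi/6 = 0.5236, and the Protocol prints 0.532. This rests only on reading ovoid as an ellipsoid with three full diameters.

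The consequences depend on a fact that the Protocol does not supply. If 0.532 was used in calculation, volumes and mean ovarian volume are 1.6% too large. If the same formula was also used for cysts, the simple-cyst limit acts at a true 59.05 cm³ and only simple cysts of 59.05 to 60 cm³ are affected. If it was not used, no volume changes.

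The constant does not enter the mortality endpoint, the sample size or the power. The same formula would serve both screened groups, so there is no reason to expect bias between them. The finding says nothing about whether 60 cm³ is the right limit.

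**What to change.** - Correct the printed coefficient under Screening tests to pi/6 (0.5236).
- Establish which constant was actually used to compute volumes, and reconcile the text with it.
- If it was 0.532, recompute reported ovarian volumes from the recorded dimensions, or multiply them by 0.984. State which coefficient was in force when the 60 cm³ limit was applied.
- If it was pi/6 or 0.523, a one-line erratum closes the point.

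Do not reclassify scans already acted on. Screening performance should describe the classification that was used at the time. The 60 cm³ rule itself stays as it is.

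The cost is one number in the text and one check of the calculation. At most, a rescaling of reported volumes follows. No new data are needed.
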